#### 8.5.3.1.1. EU-Specific Multiplicity Adjustments for the Induction Studies (Cohorts A and B)

The EU-specific hypotheses to be tested for the induction studies are outlined below.

The EU-specific primary null hypotheses to be tested:

- $H_{11}$ : The clinical remission by PRO2 rate in the filgotinib 200 mg group is equal to the clinical remission by PRO2 rate in the placebo group at Week 10
- $H_{12}$ : The endoscopic response rate in the filgotinib 200 mg group is equal to the endoscopic response rate in the placebo group at Week 10
- $H_{21}$ : The clinical remission by PRO2 rate in the filgotinib 100 mg group is equal to the clinical remission by PRO2 rate in the placebo group at Week 10
- $H_{22}$ : The endoscopic response rate in the filgotinib 100 mg group is equal to the endoscopic response rate in the placebo group at Week 10

The EU-specific key secondary null hypotheses to be tested:

- $H_{13}$ : The clinical remission by CDAI rate in the filgotinib 200 mg group is equal to the clinical remission by CDAI rate in the placebo group at Week 10
- $H_{14}$ : The clinical remission by PRO2 and endoscopic response rate (combined into a single end point at patient level) in the filgotinib 200 mg group is equal to the clinical remission by PRO2 and endoscopic response rate (combined into a single end point at patient level) in the placebo group at Week 10
- $H_{23}$ : The clinical remission by CDAI rate in the filgotinib 100 mg group is equal to the clinical remission by CDAI rate in the placebo group at Week 10
- $H_{24}$ : The clinical remission by PRO2 and endoscopic response rate (combined into a single end point at patient level) in the filgotinib 100 mg group is equal to the clinical remission by PRO2 and endoscopic response rate (combined into a single end point at patient level) in the placebo group at Week 10

[figure not shown]
Each co-primary end point for filgotinib 200 mg compared with placebo will be tested at 2-sided 0.05 significance level first. If it fails to reject the null hypothesis for at least one co-primary end point, then no further formal testings will be performed. If the null hypotheses for both co-primary end points are rejected, testing will proceed in two sequences as describe below:

- Key secondary end points for filgotinib 200 mg compared with placebo at 2-sided 0.025 significance level in a sequential order
- Each co-primary end point for filgotinib 100 mg compared with placebo at 2-sided 0.025 significance level. If the null hypotheses for both co-primary end points are rejected, then the key secondary end points for filgotinib 100 mg compared with placebo at 2-sided 0.025 significance level will be tested in a sequential order

If all the null hypotheses within the same sequence are rejected, then the respective alpha can be passed on to the other sequence. If an end point fails to reach statistical significance within the sequence, then formal testing will stop, and only nominal significance will be reported for the remaining end points.

A graphical illustration of the testing strategy for the primary and key secondary hypotheses in the Induction Studies is shown in Figure 8-1.

**Figure 8-1. Induction Studies (Cohorts A and B): Testing Strategy for the Primary and Key Secondary Hypotheses**

### 8.5.3.2. Maintenance Study

The hypotheses to be tested for the Maintenance Study are outlined below.

The primary null hypotheses to be tested:

- $H_{11}$ : The clinical remission by CDAI rate in the filgotinib 200 mg group is equal to the clinical remission by CDAI rate in the placebo group at Week 58
- $H_{12}$ : The endoscopic response rate in the filgotinib 200 mg group is equal to the endoscopic response rate in the placebo group at Week 58
- $H_{21}$ : The clinical remission by CDAI rate in the filgotinib 100 mg group is equal to the clinical remission by CDAI rate in the placebo group at Week 58
- $H_{22}$ : The endoscopic response rate in the filgotinib 100 mg group is equal to the endoscopic response rate in the placebo group at Week 58

The key secondary null hypotheses to be tested:

- H13: The clinical remission by PRO2 rate in the filgotinib 200 mg group is equal to the clinical remission by PRO2 rate in the placebo group at Week 58
- H14: The clinical response by CDAI rate in the filgotinib 200 mg group is equal to the clinical response by CDAI rate in the placebo group at Week 58
- H15: The sustained clinical remission by CDAI rate in the filgotinib 200 mg group is equal to sustained clinical remission by CDAI rate in the placebo group at Weeks 10 and 58
- H16: The 6-month corticosteroid-free remission by CDAI rate in the filgotinib 200 mg group is equal to the 6-month corticosteroid-free remission by CDAI rate in the placebo group at Week 58
- H17: The sustained clinical remission by PRO2 rate in the filgotinib 200 mg group is equal to the sustained clinical remission by PRO2 rate in the placebo group at Weeks 10 and 58
- H18: The 6-month corticosteroid-free remission by PRO2 rate in the filgotinib 200 mg group is equal to 6-month corticosteroid-free remission by PRO2 rate in the placebo group at Week 58
- H23: The clinical remission by PRO2 rate in the filgotinib 100 mg group is equal to the clinical remission by PRO2 rate in the placebo group at Week 58
- H24: The clinical response by CDAI rate in the filgotinib 100 mg group is equal to the clinical response by CDAI rate in the placebo group at Week 58
- H25: The sustained clinical remission by CDAI rate in the filgotinib 100 mg group is equal to sustained clinical remission by CDAI rate in the placebo group at Weeks 10 and 58
- H26: The 6-month corticosteroid-free remission by CDAI rate in the filgotinib 100 mg group is equal to the 6-month corticosteroid-free remission by CDAI rate in the placebo group at Week 58
- H27: The sustained clinical remission by PRO2 rate in the filgotinib 100 mg group is equal to the sustained clinical remission by PRO2 rate in the placebo group at Weeks 10 and 58
- H28: The 6-month corticosteroid-free remission by PRO2 rate in the filgotinib 100 mg group is equal to 6-month corticosteroid-free remission by PRO2 rate in the placebo group at Week 58

[figure not shown]
Each co-primary end point for filgotinib 200 mg compared with placebo will be tested at 2-sided 0.05 significance level first. If it fails to reject the null hypothesis for at least one co-primary end point, then no further formal testings will be performed. If the null hypotheses for both co-primary end points are rejected, testing will proceed in two sequences as describe below:

- Key secondary end points for filgotinib 200 mg compared with placebo at 2-sided 0.025 significance level in a sequential order
- Each co-primary end point for filgotinib 100 mg compared with placebo at 2-sided 0.025 significance level. If the null hypotheses for both co-primary end points are rejected, then the key secondary end points for filgotinib 100 mg compared with placebo at 2-sided 0.025 significance level will be tested in a sequential order

If all the null hypotheses within the same sequence are rejected, then the respective alpha can be passed on to the other sequence. If an end point fails to reach statistical significance within the sequence, then formal testing will stop and only nominal significance will be reported for the remaining endp oints.

Graphical illustrations for the testing strategies for the primary and key secondary hypotheses in the Maintenance Study are shown in [Figure 8-2](#).

**Figure 8-2. Maintenance Study: Testing Strategy for the Primary and Key Secondary Hypotheses**

8.5.3.2.1. EU-Specific Multiplicity Adjustments for the Maintenance Study

The EU-specific hypotheses to be tested for the Maintenance Study are outlined below.

The EU-specific primary null hypotheses to be tested:

- $H_{11}$ : The clinical remission by PRO2 rate in the filgotinib 200 mg group is equal to the clinical remission by PRO2 rate in the placebo group at Week 58
- $H_{12}$ : The endoscopic response rate in the filgotinib 200 mg group is equal to the endoscopic response rate in the placebo group at Week 58
- $H_{21}$ : The clinical remission by PRO2 rate in the filgotinib 100 mg group is equal to the clinical remission by PRO2 rate in the placebo group at Week 58
- $H_{22}$ : The endoscopic response rate in the filgotinib 100 mg group is equal to the endoscopic response rate in the placebo group at Week 58

The EU-specific key secondary null hypotheses to be tested:

- $H_{13}$ : The clinical remission by CDAI rate in the filgotinib 200 mg group is equal to the clinical remission by CDAI rate in the placebo group at Week 58
- $H_{14}$ : The sustained clinical remission by PRO2 rate in the filgotinib 200 mg group is equal to sustained clinical remission by PRO2 rate in the placebo group at Weeks 10 and 58
- $H_{15}$ : The clinical remission by PRO2 and endoscopic response rate (combined into a single end point at patient level) in the filgotinib 200 mg group is equal to the clinical remission by PRO2 and endoscopic response rate (combined into a single end point at patient level) in the placebo group at Week 58
- $H_{16}$ : The 6-month corticosteroid-free remission by PRO2 rate in the filgotinib 200 mg group is equal to the 6-month corticosteroid-free remission by PRO2 rate in the placebo group at Week 58
- $H_{23}$ : The clinical remission by CDAI rate in the filgotinib 100 mg group is equal to the clinical remission by CDAI rate in the placebo group at Week 58
- $H_{24}$ : The sustained clinical remission by PRO2 rate in the filgotinib 100 mg group is equal to sustained clinical remission by PRO2 rate in the placebo group at Weeks 10 and 58
- $H_{25}$ : The clinical remission by PRO2 and endoscopic response rate (combined into a single end point at patient level) in the filgotinib 100 mg group is equal to the clinical remission by PRO2 and endoscopic response rate (combined into a single end point at patient level) in the placebo group at Week 58
- $H_{26}$ : The 6-month corticosteroid-free remission by PRO2 rate in the filgotinib 100 mg group is equal to the 6-month corticosteroid-free remission by PRO2 rate in the placebo group at Week 58

[figure not shown]
Each co-primary end point for filgotinib 200 mg compared with placebo will be tested at 2-sided 0.05 significance level first. If it fails to reject the null hypothesis for at least one co-primary end point, then no further formal testings will be performed. If the null hypotheses for both co-primary end points are rejected, testing will proceed in two sequences as describe below:

- Key secondary end points for filgotinib 200 mg compared with placebo at 2-sided 0.025 significance level in a sequential order
- Each co-primary end point for filgotinib 100 mg compared with placebo at 2-sided 0.025 significance level. If the null hypotheses for both co-primary end points are rejected, then the key secondary end points for filgotinib 100 mg compared with placebo at 2-sided 0.025 significance level will be tested in a sequential order

If all the null hypotheses within the same sequence are rejected, then the respective alpha can be passed on to the other sequence. If an end point fails to reach statistical significance within the sequence, then formal testing will stop and only nominal significance will be reported for the remaining end points.

Graphical illustrations for the testing strategies for the EU-specific primary and key secondary hypotheses in the Maintenance Study are shown in [Figure 8-3](#).

**Figure 8-3. Maintenance Study: EU-Specific Testing Strategy for the Primary and Key Secondary Hypotheses**

CCI

[REDACTED]

[REDACTED]

CCI

## 8.6. Safety Analysis

Safety will be evaluated by assessment of clinical laboratory tests, physical examinations, vital signs measurements at various time points during the study, and by the documentation of AEs.

### Induction Studies (Cohorts A and B)

All safety data collected on or after the first dose of study drug administration for each Induction Study (Day 1) up to:

- 30 days after last dose date, for subjects who prematurely discontinued study drug prior to or at Week 10 OR
- Week 10, for subjects who completed Week 10 dosing and continued on study drug will be summarized by treatment group according to the study drug received.

### Maintenance Study

All safety data collected on or after the first dose of study drug administration for the Maintenance study (Week 11) up to 30 days after permanent discontinuation of study drug will be summarized by treatment group according to the study drug received.

### Overall (Induction and Maintenance)

All safety data collected on or after the first dose of study drug administration for the entire study (Day 1) up to 30 days after permanent discontinuation of study drug will be summarized by treatment group according to the study drug received.

All data collected during the course of study will be included in data listings.

#### 8.6.1. Extent of Exposure

A subject's extent of exposure to study drug will be generated from the study drug administration page of the eCRF. The number of doses administered and the level of adherence will be summarized by treatment group.

### **8.6.2. Adverse Events**

Adverse events will be coded using the Medical Dictionary for Regulatory Activities (MedDRA). System Organ Class (SOC), High-Level Group Term (HLGT), High-Level Term (HLT), Preferred Term (PT), and Lower-Level Term (LLT) will be attached to the clinical database.

Treatment-Emergent Adverse Events (TEAEs) are defined as 1 or both of the following:

#### Induction Studies (Cohorts A and B)

- Any AEs with an onset date of on or after the study drug start date for each Induction study (Day 1) and up to:
  - 30 days after last dose date, for subjects who prematurely discontinued study drug prior to or at Week 10 OR
  - Week 10, for subjects who completed Week 10 dosing and continued on study drug
- Any AEs leading to premature discontinuation of study drug prior to Week 10.

#### Maintenance Study

- Any AEs with an onset date of on or after the study drug start date for the Maintenance study (Week 11) and up to 30 days after permanent discontinuation of study drug.
- Any AEs leading to premature discontinuation of study drug after first dose of study drug administration for the Maintenance study (Week 11).

#### Overall (Induction and Maintenance)

- Any AEs with an onset date of on or after the study drug start date for the entire study (Day 1) and up to 30 days after permanent discontinuation of study drug.
- Any AEs leading to premature discontinuation of study drug.

Summaries (number and percentage of subjects) of TEAEs by SOC and PT will be provided by treatment group. TEAEs will also be summarized by relationship to study drug and severity. In addition, TEAEs leading to premature discontinuation of study drug will be summarized and listed.

### 8.6.3. Laboratory Evaluations

Selected laboratory data (using conventional units) will be summarized using only observed data. Absolute value and change from baseline at all scheduled time points will be summarized.

Graded laboratory abnormalities will be defined using the grading scheme defined in the CTCAE in [Appendix 6](#).

Incidence of treatment-emergent laboratory abnormalities defined as values that increase at least 1 toxicity grade from baseline at any time post baseline will be summarized by treatment group. If baseline data are missing, then any graded abnormality (ie, at least a Grade 1) will be considered treatment emergent.

### 8.6.4. Other Safety Evaluations

Individual data for physical examination findings, prior and concomitant medications and medical history will be provided. Twelve-lead ECGs and vital signs measurements will be listed by subject and summarized by incidence of events/abnormalities or descriptive statistics as appropriate.

### 8.7. Pharmacokinetic Analysis

For each individual study (Cohort A Induction Study, Cohort B Induction Study and Maintenance Study), plasma concentrations of filgotinib and its metabolite GS-829845 will be listed and summarized by treatment using descriptive statistics (eg, sample size, arithmetic mean, geometric mean, % coefficient of variation, standard deviation, median, minimum, and maximum). Plasma concentrations over time may also be plotted in semi-logarithmic and linear formats as mean  $\pm$  SD and median (Q1, Q3).

For subjects enrolled in the optional PK substudy, pharmacokinetic parameters of filgotinib and its metabolite GS-829845 will be listed and summarized by treatment; and plasma concentrations of the filgotinib and GS-829845 over time will be plotted in semi logarithmic and linear formats as mean  $\pm$  SD and median (Q1, Q3) by treatment.

Exposure-response relationships for efficacy and safety may also be evaluated.

CCI

[REDACTED]

CCI

## 8.9. Sample Size

### 8.9.1. Induction Studies (Cohorts A and B)

The sample size was chosen to ensure that a clinically meaningful difference in both clinical remission rate by CDAI at Week 10 and endoscopic response rate at Week 10 could be detected when comparing filgotinib 200 mg to placebo within each Induction Study.

A sample size of 220 subjects in each treatment group (n = 660 total) will provide an overall power of 97% for a filgotinib 200 mg group comparison to placebo at a 2-sided 0.05 significance level to detect a treatment difference of 20% in clinical remission rate by CDAI at Week 10 (45% on filgotinib 200 mg and 25% on placebo) and a treatment difference of 15% in endoscopic response rate at Week 10 (25% on filgotinib 200 mg and 10% on placebo). Since each end point needs to achieve statistical significance, the overall power of 97% is calculated as the product of the two individual powers based on each end point.

#### 8.9.1.1. EU-Specific Sample Size for the Induction Studies (Cohorts A and B)

The sample size was chosen to ensure that a clinically meaningful difference in both clinical remission rate by PRO2 at Week 10 and endoscopic response rate at Week 10 could be detected when comparing filgotinib 200 mg to placebo within each Induction Study.

A sample size of 220 subjects in each treatment group (n = 660 total) will provide an overall power of 93% for a filgotinib 200 mg group comparison to placebo at a 2-sided 0.05 significance level to detect a treatment difference of 15% in clinical remission rate by PRO2 at Week 10 (30% on filgotinib 200 mg and 15% on placebo) and a treatment difference of 15% in endoscopic response rate at Week 10 (25% on filgotinib 200 mg and 10% on placebo). Since each end point needs to achieve statistical significance, the overall power of 93% is calculated as the product of the two individual powers based on each end point.

### 8.9.2. Maintenance Study

Assuming an Induction response rate (ie, proportion of subjects achieving clinical remission by PRO2 or endoscopic response at Week 10) of 40% among subjects receiving filgotinib 200 mg or filgotinib 100 mg treatment, approximately 176 subjects from each filgotinib dose group from Cohorts A and B Induction Studies combined would be eligible to be re-randomized into the Maintenance Study.

The sample size was chosen to ensure that a clinically meaningful difference in both clinical remission rate by CDAI and endoscopic response rate at Week 58 could be detected when comparing filgotinib 200 mg to placebo in the Maintenance Study.

A sample size of 60 subjects in the placebo group and 120 subjects in the filgotinib group at the same dose level as the induction dose will provide an overall 94% power for a filgotinib 200 mg comparison to placebo at a 2-sided 0.05 significance level to detect a treatment difference of 30% in maintenance clinical remission rate by CDAI at Week 58 and maintenance endoscopic response rate at Week 58 (50% on filgotinib 200 mg and 20% on placebo). Since each end point needs to achieve statistical significance, the overall power of 94% is calculated as the product of the two individual powers based on each end point.

#### 8.9.2.1. EU-Specific Sample Size for the Maintenance Study

The sample size was chosen to ensure that a clinically meaningful difference in both clinical remission rate by PRO2 at Week 58 and endoscopic response rate at Week 58 could be detected when comparing filgotinib 200 mg to placebo in the Maintenance Study.

A sample size of 60 subjects in the placebo group and 120 subjects in the filgotinib group at the same dose level as the induction dose will provide an overall 94% power for filgotinib 200 mg comparison to placebo at a 2-sided 0.05 significance level to detect a treatment difference of 30% in maintenance clinical remission rate by PRO2 at Week 58 and maintenance endoscopic response rate at Week 58 (50% on filgotinib 200 mg and 20% on placebo). Since each end point needs to achieve statistical significance, the overall power of 94% is calculated as the product of the two individual powers based on each end point.

### 8.10. Data Monitoring Committee

An external DMC will review the progress of the study and perform interim reviews of safety data and provide recommendation to the Sponsor whether the nature, frequency, and severity of adverse effects associated with study treatment warrant the early termination of the study in the best interests of the participants, whether the study should continue as planned, or the study should continue with modifications.

The initial meeting will occur after approximately 100 subjects reach Week 10 in Cohorts A and B combined. Following this, subsequent meetings will occur approximately once every 4 months or at a frequency determined by the DMC.

The DMC's specific activities will be defined by a mutually agreed upon charter, which will define the DMC's membership, conduct and meeting schedule.

While the DMC will be asked to advise the Sponsor regarding future conduct of the study, including possible early study termination, the Sponsor retains final decision-making authority on all aspects of the study. If the DMC recommends stopping the study for lack of efficacy, the Sponsor's Executive team will be unblinded to confirm the DMC recommendation.

### Cohorts A and B End-of-Induction Analysis

Efficacy and safety data will be evaluated by the DMC after all subjects in both cohorts complete Week 10 dosing (or prematurely discontinue study drug but complete post-treatment assessments).

Both cohorts will be examined independently.

Taking into account data in Cohort A and Cohort B, if ALL the following 4 criteria are met for BOTH cohorts, the DMC may recommend overall study discontinuation.

- 2-sided p-value for filgotinib 200 mg vs placebo comparison is larger than 0.05 on clinical remission by CDAI at Week 10
- 2-sided p-value for filgotinib 100 mg vs placebo comparison is larger than 0.05 on clinical remission by CDAI at Week 10
- 2-sided p-value for filgotinib 200 mg vs placebo comparison is larger than 0.05 on endoscopic response at Week 10
- 2-sided p-value for filgotinib 100 mg vs placebo comparison is larger than 0.05 on endoscopic response at Week 10

If any of the above criteria is not met from either cohort, the DMC may recommend that the study continue without modification.

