#### **8.5.3.1. Induction Studies (Cohorts A and B)**

The hypotheses to be tested for the induction studies are outlined below.

The primary null hypotheses to be tested:

- $H_{11}$ : The clinical remission by CDAI rate in the filgotinib 200 mg group is equal to the clinical remission by CDAI rate in the placebo group at Week 10
- $H_{12}$ : The endoscopic response rate in the filgotinib 200 mg group is equal to the endoscopic response rate in the placebo group at Week 10
- $H_{21}$ : The clinical remission by CDAI rate in the filgotinib 100 mg group is equal to the clinical remission by CDAI rate in the placebo group at Week 10
- $H_{22}$ : The endoscopic response rate in the filgotinib 100 mg group is equal to the endoscopic response rate in the placebo group at Week 10

The key secondary null hypotheses to be tested:

- $H_{13}$ : The clinical remission by PRO2 rate in the filgotinib 200 mg group is equal to the clinical remission by PRO2 rate in the placebo group at Week 10
- $H_{14}$ : The clinical response by CDAI rate in the filgotinib 200 mg group is equal to the clinical response by CDAI rate in the placebo group at Week 10
- $H_{23}$ : The clinical remission by PRO2 rate in the filgotinib 100 mg group is equal to the clinical remission by PRO2 rate in the placebo group at Week 10
- $H_{24}$ : The clinical response by CDAI rate in the filgotinib 100 mg group is equal to the clinical response by CDAI rate in the placebo group at Week 10

Each co-primary endpoint for filgotinib 200 mg compared with placebo will be tested at 2-sided 0.05 significance level first. If it fails to reject the null hypothesis for at least one co-primary endpoint, then no further formal testings will be performed. If the null hypotheses for both co-primary endpoints are rejected, testing will proceed in two sequences as describe below:

- Key secondary end points for filgotinib 200 mg compared with placebo at 2-sided 0.025 significance level in a sequential order
- Each co-primary end point for filgotinib 100 mg compared with placebo at 2-sided 0.025 significance level. If the null hypotheses for both co-primary end points are rejected, then the key secondary end points for filgotinib 100 mg compared with placebo at 2-sided 0.025 significance level will be tested in a sequential order

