##### Cohort B Induction Study:

- Number of prior exposures to biologic agent ( $\leq 1$ , > 1) as listed in [Appendix 2](#)
- Concomitant use of oral, systemically absorbed corticosteroids at Day 1
- Concomitant use of immunomodulators at Day 1

For the Maintenance Study, a stratified CMH test will be used to compare the treatment effect between a filgotinib dose group and placebo among the subjects from Induction Cohorts A and B combined being treated with the same dose of filgotinib. The CMH test will be stratified by the following factors:

- History of exposure to a biologic agent, (Yes or No)
- Concomitant use of oral, systemically absorbed corticosteroids at maintenance baseline
- Concomitant use of immunomodulators at maintenance baseline

Stratification factors based on the clinical database will be used for the analysis. The stratified CMH chi-square p-value for each of the above comparison will be provided. Strata with low numbers of subjects might be aggregated for the analysis. The 2-sided 95% CI of clinical remission rate by CDAI and endoscopic response rate based on normal approximation method with a continuity correction will be provided for each treatment group. In addition, stratified proportion difference along with its 95% 2-sided CI using stratum-adjusted Mantel-Haenszel (MH) approach {Koch 1989} for each comparison will be provided as follows:

The stratified point estimates for difference in proportion of subjects achieving an endpoint between each filgotinib (F) treatment group and the placebo (P) group will be calculated following formula (1).

$$\hat{p}_F - \hat{p}_P = \frac{\sum W_h d_h}{\sum W_h} \quad (1)$$

where  $d_h = \hat{p}_{Fh} - \hat{p}_{Ph}$  is the difference in the proportion of subjects who achieved the endpoint between the filgotinib group and the placebo group in stratum  $h$  ( $h = 1, 2, \dots, K$ ), and  $W_h = \frac{n_{Fh}n_{Ph}}{n_{Fh}+n_{Ph}}$  is the weight based on the harmonic mean of sample size per treatment group for each stratum where  $n_{Fh}$  and  $n_{Ph}$  are the sample sizes of the filgotinib group and the placebo group in stratum  $h$ , respectively.

The 95% stratum-adjusted MH CIs will be calculated following formula (2).

$$\hat{p}_F - \hat{p}_P \pm Z_{1-\alpha/2} \cdot SE(\hat{p}_F - \hat{p}_P) \quad (2)$$

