## 6.5. Cohorts A and B End-of-Induction Analysis

After all subjects from Cohorts A and B have completed the Week 10 visit or have terminated prior to Week 10 (and completed post-treatment assessments, if applicable) and corresponding data entry is complete, an End-of-Induction safety and efficacy analysis will be performed for DMC review including cumulative safety analysis and efficacy analysis on primary endpoints. Gilead blinded statistical programmers will provide the unblinded external statistician, who is independent of Gilead and not a member of Gilead's Study Management Team, with the datasets and programs necessary to complete the analysis. The unblinded external statistician will apply the unblinded treatment codes to the datasets and generate the unblinded analysis results.

Both cohorts will be examined independently by the DMC:

Taking into account data in Cohort A and Cohort B, if ALL the following 4 criteria are met for BOTH cohorts, the DMC may recommend overall study discontinuation.

- 2-sided p-value for filgotinib 200 mg vs placebo comparison is larger than 0.05 on clinical remission by CDAI at Week 10
- 2-sided p-value for filgotinib 100 mg vs placebo comparison is larger than 0.05 on clinical remission by CDAI at Week 10
- 2-sided p-value for filgotinib 200 mg vs placebo comparison is larger than 0.05 on endoscopic response at Week 10
- 2-sided p-value for filgotinib 100 mg vs placebo comparison is larger than 0.05 on endoscopic response at Week 10

If the condition above is not met from either cohort, the DMC may recommend that the study continues without modification.

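### The end-of-Induction stop guidance uses 2-sided p-values with no direction, so a result significantly against filgotinib leaves the stop condition unmet

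*Protocol*

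**What the plan says.** Protocol 8.10, under Cohorts A and B End-of-Induction Analysis, lists four criteria. The first is "2-sided p-value for filgotinib 200 mg vs placebo comparison is larger than 0.05 on clinical remission by CDAI at Week 10". The other three have the same form for 100 mg and for endoscopic response. SAP 6.5 repeats the list with the condition "if ALL the following 4 criteria are met for BOTH cohorts, the DMC may recommend overall study discontinuation".

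The other branch reads "If any of the above criteria is not met from either cohort, the DMC may recommend that the study continue without modification" in the protocol and "If the condition above is not met from either cohort, the DMC may recommend that the study continues without modification" in the SAP. Both branches are permissive.

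Three further passages bear on direction and purpose:

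- Protocol 8.5.3.1 states the null hypotheses as equalities, for example "The clinical remission by CDAI rate in the filgotinib 200 mg group is equal to the clinical remission by CDAI rate in the placebo group".
- SAP 6.2.4 names the test: "The stratified CMH chi-square p-value for each of the above comparison will be provided". A chi-square p-value carries no sign.
- Protocol 8.10 gives the purpose of such a stop: "If the DMC recommends stopping the study for lack of efficacy, the Sponsor's Executive team will be unblinded to confirm the DMC recommendation".

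**The concern.** A 2-sided p of 0.05 or less arises when filgotinib is significantly better and equally when it is significantly worse. The rule separates the two branches by p alone. A significantly worse result therefore fails the larger-than-0.05 test, so that criterion is not met. One unmet criterion among eight is enough to defeat the stop condition.

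The rule exists to identify a lack of efficacy in both cohorts. Significant inferiority is the plainest form of that, yet as written it works against stopping. A DMC that wished to advise stopping in that situation would have to do so outside the written condition. Pre-specified guidance is meant to spare a committee that.

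**Working it through.** **Inputs.** From protocol 8.9.1: 220 subjects per arm; CDAI remission 45% on 200 mg vs 25% on placebo; endoscopic response 25% vs 10%; stated overall power 97%. From protocol 8.10 and SAP 6.5: four comparisons in each of two cohorts, each judged at 2-sided 0.05. The documents give no operating characteristics for the stop rule and no correlation between endpoints. I assume correlations of 0, 0.3 and 0.5. I use the unstratified pooled two-proportion z test in place of the stratified CMH test.

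**1. The plan's own figure.** The power is 0.9937 × 0.9869 = 0.981 without continuity correction and 0.9916 × 0.9820 = 0.974 with it. The stated 97% is reproduced and is not in dispute.

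**2. How bad a result must be to defeat the stop condition.** With x₁ and x₀ responders and p̄ = (x₁ + x₀)/440, z = [(x₁ − x₀)/220] / √[2p̄(1 − p̄)/220].

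- CDAI remission, filgotinib 38/220 (17.3%) vs placebo 55/220 (25%): p̄ = 93/440 = 0.2114; z = −0.0773/0.0389 = −1.99; p = 0.047.
- Endoscopic response, 11/220 (5%) vs 22/220 (10%): p̄ = 33/440 = 0.075; z = −0.05/0.0251 = −1.99; p = 0.046.

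Either result, for one dose in one cohort, leaves a criterion unmet.

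**3. The whole rule when filgotinib has no effect.** In each cohort the four z statistics are drawn from a multivariate normal distribution with mean 0. The two dose comparisons correlate at 0.5 because equal arms share one placebo arm. The endpoints correlate at r, and the cohorts are independent. There were 1,000,000 draws per value of r. As written, the stop condition fails if any |z| > 1.96. With a directional criterion it fails if any z > +1.96.

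| r | Fails as written | Fails with direction | Difference: wrong direction only |
|---|---|---|---|
| 0 | 0.316 | 0.169 | 0.147 |
| 0.3 | 0.309 | 0.163 | 0.146 |
| 0.5 | 0.297 | 0.155 | 0.142 |

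As a check, eight independent tests would give 1 − 0.95⁸ = 0.337 and 1 − 0.975⁸ = 0.183. The simulated values are somewhat lower, as positive correlation implies.

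**4. Illustration with a real adverse effect (assumed, not from the documents).** Suppose true CDAI remission is 15% on 200 mg vs 25% on placebo in both cohorts, with no effect elsewhere. The mean z is −0.10/√(2 × 0.20 × 0.80/220) = −2.62, and one such comparison reaches p ≤ 0.05 against filgotinib about 75% of the time. The stop condition is met about 4.5% of the time as written and 87-88% of the time with direction.

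**The case against.** The strongest reply is that no DMC would act on the literal wording. Most of it stands as a limit on the consequence:

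- **The guidance does not bind.** Both branches say *may*. Protocol 1.4 and 8.10 let the DMC advise stopping or modifying the study, and the sponsor keeps the final decision.
- **The sign would be visible.** Protocol 8.10 says "Efficacy and safety data will be evaluated by the DMC" at this look. SAP 6.5 gives the DMC an unblinded analysis of the primary endpoints. The primary analysis in SAP 6.2.4 includes response rates by arm and the difference, filgotinib minus placebo, with its confidence interval.
- **The intent is clear.** Protocol 8.5.1 and SAP 6.2.2 define success as an effect over placebo, and 8.10 speaks of lack of efficacy. Undirected equality hypotheses are ordinary shorthand in superiority testing.
- **The null figures are chance.** With no true effect there is no harm. Of the 14-15 points, 11-12 come from a single isolated negative test among eight.
- **The charter is not available.** It may already state a direction.

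This does not rescue the wording. The intent makes the error easy to see, but neither document writes it into the criteria. The criteria are the one place where a p-value alone decides which branch applies.

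A reader might also infer that the rule would expose Maintenance subjects to a failed drug. The documents do not support that. It would require a DMC to see filgotinib significantly worse and still advise continuing. The look also comes only after all subjects in both cohorts have completed Week 10 dosing or stopped, while re-randomization is at Week 11, so much Maintenance enrolment precedes it.

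**Conclusion.** The point holds as a defect in a written, non-binding rule. In both documents, one significant result against filgotinib in any of eight tests leaves the stop condition unmet and makes the continue branch available, contrary to the rule's purpose.

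If filgotinib had no effect anywhere, the stop condition would fail 30-32% of the time as written, against 16-17% with a directional criterion. The difference of 14-15 points consists of chance results in the wrong direction only. These figures rest on 220 per arm, a normal approximation and an assumed endpoint correlation of 0 to 0.5. The adverse-effect illustration rests wholly on assumed rates.

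Two stronger readings should be resisted. The percentages are not the probability that a harmful drug would be continued, because the DMC may advise stopping whichever branch applies. Nor does the rule declare harm to be evidence of activity; it merely fails to separate the two directions.

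**What to change.** In protocol 8.10 and SAP 6.5, and in the DMC charter if it repeats the rule, restate each of the four criteria so that it is met when the 2-sided p-value is larger than 0.05 **or** the estimated difference favours placebo. Equivalently, the one-sided p-value for benefit is larger than 0.025.

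The cost is one phrase in each document, with no new data or analysis. The guidance stays non-binding, and the type I error of the efficacy claims is unaffected.

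Every significant result in favour of filgotinib that prevents the stop condition today would still prevent it. That is narrower than saying the change never lowers the chance of continuing when some benefit exists. If one comparison had 50% power and the other seven no effect (assumed), the chance that the stop condition fails would fall from about 0.64 to 0.55-0.57. The cases lost are those where only a result against filgotinib had kept the study going.
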